5.3.2 Drug Concentration Measurements

5.3.2.1 Collection of Samples for Analysis

Blood Samples for Risankizumab Assay

Blood samples, approximately 3 mL, for risankizumab assay will be collected by venipuncture into appropriately labeled collection tubes at the time points specified in [Appendix C](#). Blood samples for the PK assay should be collected as closely as possible relative to the time of dosing and within 60 minutes prior to dosing. Date and exact time (to the nearest minute) of drug administration and PK and anti-drug antibody (ADA) sampling will be recorded in the source documents.

Blood Samples for Risankizumab Anti-Drug Antibody (ADA) Assay

Blood samples, approximately 3 mL, for risankizumab ADA assay will be collected at the time points specified in [Appendix C](#). Blood samples for the ADA assay should be collected as closely as possible relative to the time of dosing and within 60 minutes prior to dosing. Date and exact time (to the nearest minute) of drug administration and PK and ADA sampling will be recorded in the source documents.

The PK and ADA samples collected under previous protocol amendments may not be analyzed for PK and ADA per protocol Amendment 4 and 5.

After completion of the study, PK and ADA plasma samples may be used for further methodological investigations, e.g., stability testing.

5.3.2.2 Handling/Processing of Samples

Details for the handling and processing of the samples will be provided outside this protocol in the laboratory manual.

5.3.2.3 Disposition of Samples

The frozen plasma samples for risankizumab and risankizumab ADA assays will be packed and shipped from the study site to the Central Laboratory according to instructions in the central laboratory manual. An inventory of the samples included will accompany the package.

5.3.2.4 Measurement Methods

Plasma concentrations of risankizumab and relative titers of risankizumab ADA will be determined using validated methods under the supervision of the Bioanalysis department at AbbVie. Any additional analytes may be analyzed using non-validated methods. Plasma samples collected for risankizumab and risankizumab ADA analysis may be used for future assay development or validation activities.

The presence of ADA to risankizumab will be assessed via a tiered approach using a validated electrochemiluminescence assay (screening, confirmatory, and titration analysis as appropriate). Samples that are confirmed positive may be further characterized in a validated neutralizing antibody (NAb) assay. The ADA samples collected under previous protocol amendments may not be analyzed for NAb per protocol Amendment 4. All immunogenicity samples drawn at the visits specified in [Appendix C](#) will be analyzed.

5.3.3 Efficacy Variables

5.3.3.1 Key Variables

Key variables to be summarized at all visits:

- Proportion of subjects achieving PASI 90
- Proportion of subjects achieving the sPGA score of clear or almost clear
- Proportion of subjects achieving PASI 75
- Proportion of subjects achieving PASI 100
- Proportion of subjects achieving the sPGA score of clear

5.3.3.2 Additional Variables

- Additional variables include proportion of subjects achieving $\geq 50\%$ reduction in PASI score (PASI 50), absolute PASI of < 3 , DLQI score of 0, DLQI score of 0 or 1, a reduction of at least 5 points in DLQI, as well as change and percent change from baseline in PASI, DLQI, NAPSI, PPASI, and PSSI. Summaries will be provided at all visits that the corresponding variables are evaluated.

5.3.4 Safety Variables

Safety will be assessed descriptively based on AEs, physical examination, vital signs, local tolerability and laboratory data during the entire study.

5.3.5 Pharmacokinetic Variables

Risankizumab plasma concentrations will be determined. Descriptive statistics will be calculated for each sampling time (study visit). The number and percentage of subjects with ADA will be calculated. Additional analyses combining pharmacokinetic and ADA data from this study and other studies may be conducted if appropriate.

5.4 Removal of Subjects from Therapy or Assessment

5.4.1 Discontinuation of Individual Subjects

A subject may voluntarily withdraw from the study drug and/or study at any time. Subjects must be withdrawn from the study drug and/or study for reasons including, but not limited to, the following:

- The subject requests withdrawal from the study.
- Inclusion and exclusion criteria violation was noted after the subject started study drug, when continuation of the study drug would place the subject at risk.
- The subject becomes pregnant while on study drug.
- Malignancy, except for localized NMSC or carcinoma in-situ of the cervix

- The investigator believes it is in the best interest of the subject.
- Subject is significantly noncompliant with study procedures, which would put the subject at risk for continued participation in the trial.
- Clinically significant abnormal laboratory results or AEs, which rule out continuation of the study drug, as determined by the investigator or the AbbVie Therapeutic Area Medical Director.
- Post-Baseline occurrence of one or more of the following hepatic test abnormalities (confirmed on a second separate sample at least 48 hours apart):
 - ALT or AST > 8 × ULN
 - ALT or AST > 5 × ULN for more than 2 weeks
 - ALT or AST > 3 × ULN and (TBL > 2 × ULN or INR > 1.5)
 - ALT or AST > 3 × ULN with the appearance of fatigue, nausea, vomiting, right upper quadrant pain or tenderness, fever, rash, and/or eosinophilia (> 5%)
- If prohibited medication is used during the study for any indication, the subject must discontinue the use of the prohibited medication if he/she wants to continue on study drug. In case of undue safety risk for the subject, the subject should discontinue study drug at the discretion of the investigator.
- If the subject received a live virus vaccination during the study, the subject must discontinue study drug.
- If the subject develops laboratory evidence of or is known to be infected with HIV, hepatitis B or hepatitis C, the subject must be discontinued from the study drug and undergo early EOT Visit activities. Additionally, all subjects who develop laboratory evidence of infection with HIV, hepatitis B or hepatitis C must be referred to an appropriate clinician for management of their viral infection according to medical standards.
- Subject develops active TB at any time during the study.
- If the subject experiences an intolerable increase of psoriasis during the course of the study the subject will be discontinued from the study drug to receive rescue treatment as deemed appropriate by the investigator.
- If the subject experiences a serious infection, the study drug should be held until the infection is resolved or stabilized. The study drug dosing visit could

be postponed such that the study drug of the following visit will not be administered within 14 days. If the subject has not received study drug due to this serious infection for at least 24 weeks, the subject will be permanently withdrawn from study drug.

If, during the course of study drug administration, the subject prematurely discontinues study drug use, the subject has the option to continue in the study and complete the remaining visits as scheduled. If remaining visits will be completed, an early EOT visit is not required. If the subject does not continue in the study, the procedures outlined for the early EOT visit must be completed, ideally within 2 weeks of the decision and preferably prior to the initiation of another therapy. However, these procedures should not interfere with the initiation of any new treatments or therapeutic modalities that the Investigator feels are necessary to treat the subject's condition. For subjects that prematurely discontinue, study drug will not be given at the early EOT visit and subjects should have the telephonic EOO visit, 20 weeks after their last administered dose of study drug to determine the status of any ongoing AEs/SAEs or the occurrence of any new AEs/SAEs.

Following discontinuation of the study drug, the subject will be treated in accordance with the Investigator's best clinical judgment.

All attempts must be made to determine the primary reason for premature discontinuation. The information will be recorded on the appropriate eCRF page.

For subjects that are considered lost to follow-up, reasonable attempts must be made to obtain information on the final status of the subject. At a minimum, two phone calls must be made and one certified letter must be sent and documented in the subject's source documentation.

Interruption/Discontinuation of Study Drug Due to COVID-19

For subjects with documented COVID-19, the timing of next administration of study drug or possibility of premature discontinuation from study drug should be discussed with the AbbVie Medical Contact.

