5.2.3.1 Prohibited Therapy

Use of the following therapies are prohibited from administration of the first dose of study drug in the preceding study throughout the EOT visit of Study M15-997, including any gap between the preceding study and Study M15-997:

- Investigational devices or products
- anti-IL-12/23, and anti-IL-17 agents, including but not limited to guselkumab, tildrakizumab, ustekinumab, ixekizumab and secukinumab; only comparator drug use in previous study is allowed for ustekinumab

- TNF inhibitors; only comparator drug use in preceding study is allowed for Adalimumab (Humira®)
- Topical treatment for psoriasis or any other skin condition such as retinoids, vitamin D analogues, vitamin A analogs, anthralin and steroids. Exception: Lower potency topical steroids such as alclometasone dipropionate cream, ointment 0.05, desonide cream, gel, foam, ointment 0.05, fluocinolone acetonide cream, solution 0.01, dexamethasone cream 0.1, hydrocortisone cream, lotion, ointment, solution 0.25, 0.5, 1, or hydrocortisone acetate cream, ointment 0.5 - 1 may be used for limited period of time defined as approximately 6 weeks without removing subjects from the study with a restriction of use within 24 hours prior to study visit.
- Systemic immunomodulating medications including methotrexate (MTX), cyclosporine A and corticosteroids except steroids with only a topical effect (e.g., inhalative corticosteroids to treat asthma or drops used in the eye or ear)
- Systemic psoriasis medications including retinoids and fumarates, or any other drugs known to possibly benefit psoriasis
- Photochemotherapy (e.g., PUVA)
- Phototherapy (e.g., UVA, UVB, Ultra Violet A/B)
- Live vaccines (Live vaccines are not permitted up to 20 weeks after the last dose of study drug).

The AbbVie TA MD should be contacted if there are any questions regarding prohibited therapy.

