6.1.1 Definitions

6.1.1.1 Adverse Event

An adverse event (AE) is defined as any untoward medical occurrence in a patient or clinical investigation subject administered a pharmaceutical product and which does not necessarily have a causal relationship with this treatment. An AE can, therefore, be any unfavorable and unintended sign (including an abnormal laboratory finding), symptom, or disease temporally associated with the use of a medicinal (investigational) product, whether or not the event is considered causally related to the use of the product.

Such an event can result from use of the drug as stipulated in protocol or labeling, as well as from accidental or intentional overdose, drug abuse, or drug withdrawal. Any worsening of a pre-existing condition or illness is considered an AE. Worsening in severity of a reported AE should be reported as a new AE. Laboratory abnormalities and changes in vital signs are considered to be AEs only if they result in discontinuation from the study, necessitate therapeutic medical intervention, and/or if the investigator considers them to be AEs.

An elective surgery/procedure scheduled to occur during a study will not be considered an AE if the surgery/procedure is being performed for a pre-existing condition and/or the surgery/procedure has been pre-planned prior to study entry. However, if the pre-existing condition deteriorates unexpectedly during the study (e.g., surgery performed earlier than planned), then the deterioration of the condition for which the elective surgery/procedure is being done will be considered an AE.

Prior to use, every attempt should be made to contact the AbbVie TA MD for direction on re-introduction of study drug therapy after prohibited medication administration.

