7.4 Protocol Deviation

Number and percentage of subjects who reported at least one of the following protocol deviation categories will be provided in the ALL_RZB Population.

- Subject entered into the study even though she/he did not satisfy entry criteria
- Subject who developed withdrawal criteria during the study and was not withdrawn
- Subject who received wrong treatment or incorrect dose
- Subject who received excluded or prohibited concomitant medication?

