10.0 Efficacy Analysis

10.1 General Considerations

The efficacy analysis will be performed for each population except the ALL_RZB Population. The efficacy analysis will use the data from this study and preceding study after subjects started to take risankizumab. The BL values (baseline values from the

preceding studies) will be used to determine responses and changes in the efficacy variables.

Continuous variables will be summarized by the number of observations, mean, standard deviation, median, minimum, maximum, 25th and 75th percentiles, as well as the 95% confidence intervals (CIs) of the mean values. Categorical variables will be summarized by counts and percentages, as well as the 95% CIs of the percentages. No statistical tests will be performed in this study.

Missing data will be imputed using the following methods for the efficacy analyses:

- Last Observation Carried Forward (LOCF): The LOCF analyses will use the last observed non-missing evaluation (last completed non-missing evaluation, from composite endpoint) from the previous visit within the particular period for efficacy measures assessed to impute missing data at later visits in the same period. Baseline efficacy evaluations will not be carried forward. Of note, post-baseline observations from Part A1 in Study 1311.4 can be carried forward to ITT_A2 subjects from ARM 1 since treatment is the same.
- As-Observed Cases (OC): The as-observed analysis will not impute values for missing evaluations, and thus a subject who does not have an evaluation on a scheduled visit will be excluded from the as-observed analysis for that visit.

LOCF will be used as the primary imputation method and OC will be used as sensitivity analysis for both categorical variables and continuous variables. Both LOCF and OC will not include values after discontinuation of study drug.

All endpoints will be analyzed up to the last visit with at least one subject has observed measurements of that variable, by the time of the interim data cutoff.

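### The SAP has no rule for efficacy values taken during or soon after prohibited psoriasis therapy in subjects who stay on study drug, so LOCF and OC both count them as risankizumab results

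*Protocol*

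**What the plan says.** Protocol 5.2.3.1 states: "Use of the following therapies are prohibited from administration of the first dose of study drug in the preceding study throughout the EOT visit". The list that follows includes other biologics, phototherapy, most topical psoriasis treatments and "Systemic psoriasis medications including retinoids and fumarates, or any other drugs known to possibly benefit psoriasis". Certain lower-potency topical steroids are excepted for about 6 weeks, provided they are not used in the 24 hours before a visit.

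Protocol 5.4.1 sets out what happens after a breach: "the subject must discontinue the use of the prohibited medication if he/she wants to continue on study drug". Stopping study drug is required at that point only where there is undue safety risk, at the investigator's discretion. Protocol 6.1.1.1 likewise asks sites to seek the sponsor's "direction on re-introduction of study drug therapy after prohibited medication administration". A separate item in 5.4.1 takes a subject with intolerable worsening of psoriasis off study drug so that rescue can be given.

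Protocol 8.1.4 leaves data handling for efficacy to the SAP. SAP 10.1 makes LOCF primary and OC the sensitivity analysis, with one exclusion: "Both LOCF and OC will not include values after discontinuation of study drug". Use of prohibited medication appears in two descriptive outputs. SAP 7.4 counts subjects under "Subject who received excluded or prohibited concomitant medication", and SAP 7.3 tabulates concomitant medications by generic name. Both use the ALL_RZB population, the one population for which SAP 10.1 plans no efficacy analysis.

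**The concern.** Long-term efficacy is the secondary objective, and the response rates over 252 weeks are the figures readers will take from it. Added psoriasis therapy is most likely in subjects whose response is slipping. If such a subject uses a prohibited agent, improves, stops it and stays on risankizumab, the improved PASI or sPGA is credited to risankizumab and the loss of response is hidden.

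The plan is also uneven. It discards values once study drug stops but keeps values obtained with a second active therapy on board. The 24-hour restriction on permitted topical steroids shows that the protocol recognises that other treatment can affect an assessment.

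No planned output would show the problem. LOCF and OC both use the value, and neither the medication table nor the deviation count is linked to visits or efficacy populations.

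**Working it through.** The plan gives no figure to reproduce: there is no test, no power calculation and no rate of prohibited-medication use. The check has two parts.

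**Following one value through the rules**

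1. A subject on study drug uses a prohibited psoriasis therapy, stops it and continues on study drug (Protocol 5.4.1).
2. A PASI is recorded during or soon after that use. Study drug has not been discontinued, so the SAP 10.1 exclusion does not apply.
3. OC uses the value at its visit. LOCF uses it there too, and can carry it to later missing visits in the same period.
4. Late in the study one value covers a long stretch. Visits are 24 weeks apart after Week 156, and the Week 232 window in SAP Table 1 runs from day 1542 to day 1709, which is 1709 - 1542 + 1 = 168 days.
5. If worsening is intolerable, the subject is taken off study drug before rescue, and SAP 10.1 then excludes later values. That route is already covered.

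**Size and direction**

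Let f be the share of subjects affected at a visit, r_after their response rate on the retained values, r_before their response rate on the last value before use, and p the response rate in everyone else. None of these is in the documents; all values below are assumed.

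With the values kept, the reported rate is (1 - f) × p + f × r_after. Its difference from each alternative is:

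- scoring them as non-response: f × r_after, never negative;
- carrying forward the value from before use: f × (r_after - r_before), either sign;
- dropping the affected subjects at that visit: f × (r_after - p), either sign.

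Against non-response scoring, the range is 0.02 × 0.50 = 1.0 point to 0.10 × 0.85 = 8.5 points.

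With f = 5% and p = 85%, in percentage points:

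| r_after | r_before | vs non-response | vs value before use | vs dropping |
|---|---|---|---|---|
| 90% | 0% | +4.50 | +4.50 | +0.25 |
| 70% | 30% | +3.50 | +2.00 | -0.75 |
| 50% | 50% | +2.50 | 0.00 | -1.75 |
| 40% | 80% | +2.00 | -2.00 | -2.25 |
| 0% | 90% | 0.00 | -4.50 | -4.25 |

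For example, the second row is 0.05 × 0.70 = 3.50, 0.05 × (0.70 - 0.30) = 2.00 and 0.05 × (0.70 - 0.85) = -0.75.

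The first difference is an upper bound on the bias. If a share r_alone of the affected subjects would have met the endpoint on risankizumab alone, the bias is f × (r_after - r_alone), which cannot exceed f × r_after.

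**The case against.** The strongest reply is that this is not a sanctioned add-on route. The therapies are prohibited, 5.4.1 only says what follows a breach, and the most informative case, intolerable worsening, already leads off study drug and out of the efficacy data. The rule is also not specific to psoriasis. It reads "If prohibited medication is used during the study for any indication, the subject must discontinue the use of the prohibited medication", and the list covers agents with other uses: "Systemic immunomodulating medications including methotrexate (MTX), cyclosporine A and corticosteroids except steroids with only a topical effect". In a descriptive, single-arm study, reporting values regardless of concomitant medication is a legitimate choice if it is stated. Non-response scoring is a different estimand, and stricter than the SAP's treatment of subjects who discontinue.

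Most of this stands, and it limits the point to off-protocol use short of intolerable worsening. It does not close the gap, because the SAP does not state that choice and gives no way to see how many responses are affected.

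A reader might infer more than the documents support:

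- That the protocol lets subjects take these therapies. It does not; 5.2.3.1 prohibits them.
- That keeping the values can only favour risankizumab. That is true by construction against non-response scoring. Against the value before use, or against dropping the subject, the sign can be negative, for instance when the medication was for another condition or the subject worsened despite it.
- That only late response rates are affected. Nothing confines the problem to late visits.
- That the deviation count is the only output. SAP 7.3 also tabulates the medications, though without a link to efficacy.

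**Conclusion.** The gap is real but narrower than it first looks. For subjects who use a prohibited psoriasis therapy and remain on study drug, neither document says how PASI and sPGA values are handled, so both planned analyses attribute them to risankizumab. If the therapy is effective, the likely direction is upward, at any affected visit. The sensitivity analysis cannot reveal it, because OC and LOCF share the treatment.

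The size is unknown. The 1.0 to 8.5 points rests on an assumed 2-10% affected and 50-85% of those meeting the endpoint. It counts every such response as false, so it is an illustrative upper bound and not an estimate. With no such use the effect is zero. The change is worth making because it costs little and the documents offer no other way to judge whether the effect matters.

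**What to change.** Leave the primary analysis unchanged. In SAP 10.1, add one supplementary responder analysis of the key PASI and sPGA variables:

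- Values from the start of a prohibited therapy with psoriasis activity until a pre-specified window after its end are scored as non-response and are not carried forward by LOCF. The window could be one 12-week dosing interval. It is an analysis convention, not a clinical rule, and the sponsor may fix another in advance.
- The qualifying medications are identified from the concomitant-therapy data before efficacy values are examined. Protocol 5.2.3 already requires reason for use and start and end dates. Lower-potency topical steroids used as 5.2.3.1 allows do not count.
- The number of affected subjects and visits is reported for each efficacy population.

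The cost is SAP wording, one extra table and a slightly less favourable supplementary rate. It also needs medication dates matched to visits, which goes beyond the subject count in SAP 7.4. Because efficacy summaries include preceding-study data, the SAP should say whether the rule applies there too; the documents do not show how medication was recorded in those studies.
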